3.0 Animal Studies and Previous Human Studies

Oxygen administration increases the production of F_2 -isoprostanes and isofurans *in vitro* and in mice (Figure 1).² In 435 patients from the Statin AKI Cardiac Surgery RCT we recorded oxygen administration (FIO_2) and SpO_2 prior to anesthetic induction (baseline), at induction of anesthesia, during cardiopulmonary bypass or off-pump coronary artery bypass grafting, following cardiopulmonary bypass or off-pump coronary artery bypass grafting, at ICU admission, 6-hours after ICU admission, and on postoperative day 1. In five of these subjects we maintained physiologic tissue oxygenation during surgery by limiting supplemental oxygen administration to that required to maintain $SpO_2 > 94\%$ and a $PaO_2 > 70$ mmHg (Figure 2). By doing so, both hyperoxia and hypoxia were avoided.

[figure not shown]
[figure not shown]
[figure not shown]

Figure 2
Hemoglobin Oxygen Saturation during Surgery

[figure not shown]

Fraction of Inspired Oxygen during Surgery

Oxidative stress, as measured by plasma concentrations of F_2 -isoprostanes and isofurans, was lower in the subjects administered physiologic oxygen concentrations compared to subjects who received hyperoxia, matched for risk factors for increased oxidative stress including smoking, body mass index (BMI), and use of cardiopulmonary bypass (Figure 3). In addition, none of these physiologic oxygenation preliminary subjects suffered from AKI or delirium following surgery, and duration of hospitalization was 6.3 ± 1.6 (median 5.5) days compared to 8.4 ± 4.4 (median 7) in risk-matched controls ($P < 0.001$).

Figure 3

4.0 Inclusion/Exclusion Criteria

Inclusion Criteria:

- Age \geq 18 years.
- Open-heart cardiac surgery, defined as surgery on the heart or aorta that requires sternotomy or thoracotomy.

Exclusion Criteria:

- Current acute coronary syndrome (defined as ST elevation myocardial infarction or non-ST elevation myocardial infarction (troponin leak within 72 hours of surgery +/- EKG changes consistent with myocardial ischemia)).
- Home supplemental oxygen use.
- Preoperative supplemental oxygen requirement to maintain SpO_2 of 92%.
- Right to left intracardiac shunt including atrial septal defect and ventricular septal defect with Cor Pulmonale.
- Carotid stenosis defined as $>50\%$ stenosis.
- Cardiac surgery that requires intraoperative circulatory arrest, such as aortic arch replacement.
- Current use of hemo- or peritoneal dialysis.
- Pregnancy

5.0 Enrollment/Randomization/Blinding

Patients scheduled for open-heart surgery will be screened via StarPanel. Research personnel will request an introduction from the subject's physician. If the subject agrees to the introduction, research personnel will meet with eligible study candidates during their preoperative surgical and / or anesthesia clinic appointment or on the hospital ward. Following explanation of the protocol and documented

informed consent, patients will be randomized to 1) usual care (administration of 100% FIO₂ during surgery and 80% inspired oxygen during cardiopulmonary bypass) or 2) maintenance of physiologic oxygenation (the minimum FIO₂ required to maintain SpO₂ of 95%, but no less than that of air [21%]) during surgery. The intervention is restricted to intraoperative patient management, and upon admission to the ICU after surgery all patients will be ventilated with 40% FIO₂ or the minimum required to maintain SpO₂ 95% if greater than 40%. Regardless of treatment group, all subjects will receive 100% oxygen during induction of anesthesia until tracheal intubation and lung ventilation are verified and during transport from the operating room to the ICU. Patients, laboratory technicians, statisticians and ICU staff but not anesthesiologists, perfusionists, and respiratory therapists will be blinded to treatment group. Preoperative, intraoperative, and postoperative care will remain unaffected by inclusion in this study or by study group assignment aside from administration and monitoring of oxygenation.

The study's statistician will be responsible for centralized randomization and subject assignment based on stratification in a permuted block fashion, using a sequence of blocks with sizes either two or four, where the sizes are selected uniformly at random. Randomization will be stratified by chronic kidney disease (defined as stage 3, 4, or 5 CKD [i.e., an eGFR <60 ml/min/1.73m²]) and use of cardiopulmonary bypass during surgery.

Study anesthesiologists and perfusionists will be responsible for protocol-directed administration of hyper- or physiologic oxygenation. Therefore, anesthesiologists and perfusionists will be aware of subject treatment assignment. We do not expect knowledge of treatment assignment by anesthesiologists or perfusionists to affect other aspects of intraoperative management, including medication or fluid administration. We expect subjects randomized to physiologic oxygenation or hyper-oxygenation to behave the same (similar vital signs, similar responses to surgery, similar response to medications, etc.) and to not warrant any differences in care based on treatment assignment. Operating room surgeons will not be informed of subject assignment, but we will not initiate any procedures such as concealing oxygen and air flow meters to actively blind them from assignment. We do not expect any knowledge of subject treatment assignment by surgeons to affect their treatment of subjects. Study subjects, ICU nurses, intensivists, laboratory technicians, and statisticians will be blinded to treatment assignment throughout subject study. To ensure blinding of ICU intensivists and staff, anesthesiologists will withhold treatment group assignment at the time of subject transfer of care at the end of surgery. Objective endpoints such as laboratory values will be measured by technicians and co-investigators blinded to treatment assignment. Clinical endpoints such as wound infection and delirium will be measured by physicians and research staff blinded to treatment assignment. The key that lists the treatment of each subject will be withheld from investigators, laboratory technicians, and statisticians until the dataset is locked. All preoperative, intraoperative, and postoperative clinical care will be administered according to standardized clinical protocol and will not be affected by inclusion in this study or by study group assignment.

6.0 Study Procedures

We will study 200 adult cardiac surgery patients and randomize them to either hyper-oxygenation during or physiologic oxygenation during cardiac surgery.

Once we have obtained informed consent, we will collect baseline data from the medical record. Upon arrival in the operating room, subjects will be placed on American Society of Anesthesiologists universal monitors as per standard care.

Oxygen administration and monitoring during and following surgery:

1. Hyper-oxygenation control group (usual care):

- Subjects will be preoxygenated with 100% FIO₂ prior to induction of anesthesia.
- Following induction of anesthesia and verification of tracheal intubation and lung ventilation, subjects will be ventilated with 100% oxygen with a tidal volume of 8 ml/kg ideal body weight, respiratory rate titrated to an end-tidal partial pressure of CO₂ of 35 cm H₂O, and positive end-expiratory pressure of 5 mmHg.
- During cardiopulmonary bypass, the oxygenator in the cardiopulmonary bypass circuit will be ventilated with 80% oxygen and gas flow titrated to achieve an arterial blood partial pressure of CO₂ of 50 mmHg. FIO₂ during cardiopulmonary bypass may be increased (see "Titration of FIO₂ during surgery" below).
- During transport from the operating room to the intensive care unit (ICU) following surgery, subjects will be connected to an Ambu bag and mechanically ventilated with 6 liters oxygen per minute fresh gas flow.
- Upon arrival in the ICU, subjects will be placed on the ICU ventilator and ventilated with 40% oxygen with a tidal volume of 8 ml/kg of ideal body weight, respiratory rate of 12 breaths per minute, and positive end-expiratory pressure of 8 mmHg, as is usual practice.
- Subsequent mechanical ventilation, supplemental oxygen administration, and subject extubation will be at the discretion of the ICU intensivist.

2. Physiologic oxygenation group:

- Subjects will be preoxygenated with 100% FIO₂ prior to induction of anesthesia (similar to hyper-oxygenated group subjects).
- Following induction of anesthesia and verification of tracheal intubation and lung ventilation, subjects will be ventilated with 21% oxygen with a tidal volume of 8 ml/kg ideal body weight, respiratory rate titrated to an end-tidal partial pressure of CO₂ of 35 cm H₂O, and positive end-expiratory pressure of 5 mmHg. FIO₂ during lung ventilation may be increased and subsequently decreased in order to maintain SpO₂ between 95-97 % (see "Titration of FIO₂ during surgery" below).
- During initiation of cardiopulmonary bypass, the oxygenator in the cardiopulmonary bypass circuit will be ventilated with 60% FIO₂ and the gas flow titrated to achieve an arterial blood partial pressure of CO₂ of 50 mmHg. Immediately following achievement of full flow on cardiopulmonary bypass, the FIO₂ will be decreased to achieve a SpO₂ between 95-97%, and an arterial blood gas sample will be measured to titrate the inline co-oximeter. Subsequent FIO₂ titrations during cardiopulmonary bypass will be made using the inline co-oximeter to achieve target PaO₂ 80-110 mmHg (see "Titration of FIO₂ during surgery" below).
- During transport from the operating room to the ICU following surgery, subjects will be connected to an Ambu bag and mechanically ventilated with 6 liters oxygen per minute fresh gas flow (similar to hyper-oxygenated group subjects).
- Upon arrival in the ICU subjects will be placed on the ICU ventilator and ventilated with 40% oxygen or the same FIO₂ the patient was being ventilated at the completion of surgery (whichever is higher), with a tidal volume of 8 ml/kg ideal body weight, respiratory rate of 12 breaths per minute, and positive end-expiratory pressure of 8 mmHg.
- Subsequent mechanical ventilation, supplemental oxygen administration, and subject extubation will be at the discretion of the ICU intensivist.

Titration of FIO₂ during surgery (for both the hyper-oxygenation and physiologic oxygenation groups):

Throughout the course of intervention, which runs from post anesthetic induction to transfer of care to the ICU staff, the subject's anesthesiologist will continuously monitor the subject's SpO₂ with every beat of the heart, as is standard care. During cardiopulmonary bypass the subject's perfusionists will continuously monitor the subject's PaO₂ with real-time inline co-oximetry, as is standard care. Anesthesiologists and perfusionists are intimately familiar with monitoring patient oxygenation and titrating oxygen delivery. The maintenance of perfusion and tissue oxygen delivery is the most basic responsibility of anesthesiologists and perfusionists.

During lung ventilation, if a subject's SpO₂ falls below 95% for 1 minute, the anesthesiologist will increase the FIO₂ by 10%. If the SpO₂ rises to > 97%, the anesthesiologist will decrease the FIO₂ by 10%. If the anesthesiologist determines the subject requires more than a 10% change in FIO₂, the adjustment of the FIO₂ is at the discretion of the anesthesiologist. The anesthesiologist will wait 2 minutes between changes in FIO₂ unless the anesthesiologist determines the subject requires more rapid titration of FIO₂ to maintain target SpO₂ 95-97%. A fresh gas flow of 2 liters/minute will be maintained throughout surgery.

During cardiopulmonary bypass, if a subject's arterial oxygen tension falls below 80 mmHg, the perfusionist will increase the FIO₂ by 10%. If the SpO₂ rises above 110 mmHg, the perfusionist will decrease the FIO₂ by 10%. If the anesthesiologist or perfusionist determines the subject requires more than a 10% change in FIO₂, the adjustment of the FIO₂ is at the discretion of the anesthesiologist and perfusionist. The perfusionist will wait 2 minutes between changes in FIO₂ unless the anesthesiologist or perfusionist determines the subject requires more rapid titration of FIO₂ to maintain target PaO₂ 80-110 mmHg.

We will evaluate the following endpoints (primary, secondary, and safety endpoints):

1. Postoperative creatinine change from baseline to postoperative day 2 (Aim 1 primary endpoint). Serum creatinine will be measured daily during hospitalization.
2. Additional markers of AKI including incidence of AKI using KDIGO criteria and urinary markers NGAL and IGFBP-7/TEMP-2.²⁴
3. Incidence and duration of delirium, measured using the Confusion Assessment Method for the ICU (CAM-ICU) twice daily while in the ICU or for at least 3 days postoperatively.²⁵
4. Oxygen administration, tissue oxygenation, and perfusion, specifically SpO₂ (median +/- 95% CI and area-under-the-curve (AUC) < 90%), PaO₂ (median +/- 95% CI, AUC > 150 mmHg, and AUC < 70 mmHg), brain and muscle O₂ saturation (median +/- 95% CI and AUC < 80% baseline), the percent of FIO₂ titrations within protocol (protocol adherence), cardiac output using a PA catheter placed as part of usual care, mixed venous hemoglobin O₂ saturation, and arterial lactate.
5. Oxidative stress. We will measure F₂-isoprostanes/isofurans (Aim 2 primary endpoint) prior to surgery, during surgery, and following surgery.
6. Reactive oxygen species production using electron spin probes and electron paramagnetic resonance and dihydroethidium and HPLC in blood, myocardium, and epicardial fat.
7. Vascular reactivity (Effects on Endothelial Function sub-study). We will measure flow mediated dilation of the brachial artery using ultrasound and peripheral tonometry with wrist or finger probes before and after inflating a blood pressure cuff, and we will measure vasoconstriction and relaxation in blood vessels dissected from epicardial fat and distal mammary artery that is removed and discarded by the surgeon as part of standard cardiac

surgery in a subset of patients chosen at random (n=40). We will quantify markers of endothelial activation in plasma including PAI-1 and E-selectin.

8. Mitochondrial function. We will measure markers of mitochondrial function including superoxide production, mitochondrial DNA content, mitochondrial membrane potential, PGC-1a mRNA expression, and mitochondrial respiration in PBMCs isolated from blood and atrial tissue resected by the surgeon as part of standard cardiac surgery.
9. Other ICU morbidities including the time to extubation, development of arrhythmias including atrial fibrillation, dialysis, pneumonia (defined as a positive sputum culture or postoperative pulmonary infiltrate with systemic signs of infection [temperature >38.6°C or white blood cell count >12.0 × 109/L] and the use of parenteral antibiotics or documentation of the diagnosis by the patient's physician), wound infection (CDC criteria), and ICU length of stay.
10. Pain assessment on postoperative day 5 and at one year, using the Numeric Rating Scale (NRS) 0-10 pain assessment and the short-form McGill Pain Questionnaire.
11. One year follow-up data including assessments of cognitive function (Short Blessed Test), activities of daily living, and depression (Center for Epidemiologic Studies-Depression (CES-D) test will be obtained by phone interview, and we will examine the clinical chart for admissions, events (any renal replacement therapy), and laboratory findings (with particular focus on serum creatinine, eGFR, and urine proteinuria) in this period.
12. Safety endpoints will focus on any risk of hypoxia between study groups and will include postoperative day 1 serum CK-MB measurements (myocardial injury, defined as CK-MB greater than 50 ng/mL [10 times the upper limit of normal] and CK-MB as a continuous endpoint), postoperative myocardial infarction [defined by a new Q-wave on EKG], rates of reintubation, transient ischemic attack [defined as new deficit on neurologic exam that abates within 72 hours], stroke [defined as new deficit on neurologic exam and confirmed with radiological evidence], and death.

Urine, blood, and tissue use:

Following the placement of the arterial line and Foley catheter, 20 mL of blood and 20 mL of urine will be collected at the induction of anesthesia (baseline). We will also collect 15 mL blood and 20 mL of urine during cardiopulmonary bypass or off-pump coronary artery bypass for those subjects not requiring cardiopulmonary bypass, following cardiopulmonary bypass or off-pump coronary artery bypass, at ICU admission, 6 hours after ICU admission, and on postoperative day 1 and day 2. In total we will collect 110 mL of blood and 140 mL urine. When, after dissection of the pericardial fat, mammary artery, and incision of the atria as part of standard cardiac surgery, 1-2 g of redundant atrial tissue, 1-2 grams of discarded fat, and 1-2 g of discarded distal mammary artery will be collected for measurement of atrial myocardial function, inflammation, amyloid, oxidative stress, and arteriole vascular reactivity. Typically, this tissue is discarded, but instead we will harvest this tissue at the end of surgery. We used the same technique for collection of tissue in 450 cardiac surgery subjects in the Atrial Fibrillation and Renin Angiotensin Aldosterone System (RAAS) study (PI: [name]).²⁶

We will also collect data regarding vital signs, electroencephalographic activity, medication use, fluid input and urine output, clinical labs, and postoperative outcomes.

Sample Time-course:

- Preoperative: The PI or his research nurse will offer study participation to adult patients

undergoing cardiac surgery after patients express interest to their surgeon in conjunction with a patient's preoperative surgical consultation appointment, preanesthetic evaluation appointment, or on the hospital ward. We successfully recruited subjects in these venues for 653 patients enrolled in the Statin AKI Cardiac Surgery RCT (PI: [name]).²⁷ After obtaining informed consent, patients will undergo a brief neuropsychological assessment that will include the Mini Mental Status test, the Trails B test, the CES-D Test, and the NRS 0-10 pain assessment. Patient demographics and past medical history will be documented.

- Day of surgery: anesthesia, surgery, and ICU admission will proceed irrespective of the subject's participation in the study except for the oxygen administration and monitoring and sample collection described above. Study intervention will occur in the operating room and will terminate when subject care is transferred from the anesthesiologist to the intensivist following admission to the ICU.
- Postoperative: subject postoperative ICU and hospital ward stay will proceed irrespective of the subjects' participation in the study and will be controlled by the subject's surgeon, intensivist, and consultants. Patients will be evaluated twice daily while in the ICU or for the first 3 days following surgery for level of sedation using the Richmond Agitation-Sedation Scale (RASS)²⁸ and for delirium using the CAM-ICU. Both of these assessments are standard practice in the ICUs at VUMC. On postoperative day 5 we will assess patients pain using the NRS 0-10 pain scale and the short-form McGill Pain Questionnaire.
- Subject discharge will proceed irrespective of study. In the Statin AKI Cardiac Surgery RCT, median hospital length of stay was 7 days.
- One year following surgery, we will call patients to conduct a phone interview in which we will assess neuropsychological function and activities of daily living including NRS 0-10 pain scale, short-form McGill Pain Questionnaire, the Short Blessed Test, and the CES-D Test. This assessment will take about 15 minutes to complete.

Data and Safety Monitoring Board (DSMB):

The DSMB will provide objective review of the treatment results as they relate to human safety and data quality. [REDACTED] have agreed to serve on the committee. [REDACTED], who will serve as chair, is [REDACTED]

[REDACTED]

The DSMB will receive report on the progress, adverse events, safety endpoints, and clinical outcomes at each interim analysis from the PI and the statistician. The first planned interim analyses will occur after 20 (11.1%) subjects have been studied and discharged from the hospital following surgery. At this meeting, the DSMB will evaluate subject recruitment, the documentation of subject data, and the collection and reporting of adverse events, serious adverse events, and safety endpoints. The DSMB will also evaluate any study withdrawals, any adverse events, in-hospital all-cause mortality, and safety outcomes (stroke, TIA, or Q-wave myocardial infarction).

The second planned interim analyses will occur after 100 (50%) subjects have been studied and discharged from the hospital following surgery. At this meeting, the DSMB will evaluate any study withdrawals, any adverse events, in-hospital all-cause mortality, safety outcomes (stroke, TIA, or Q-wave myocardial infarction), and a conditional power analysis implemented by the study statistician. The conditional power analysis will assess the likelihood of rejecting the null hypotheses (for the primary endpoints of Aims 1 and 2) at the study conclusion (N=200), assuming that the effect of intervention is as large or larger than the estimated effect at the second interim analysis (N=100). To do so, the study statistician will compare mock-unblinded data (A vs. B, where it remains unknown if A or B is normoxia or

hyperoxia). If the conditional power is less than the original target (80%), the DSMB will consider recommending an increase in the study sample size to achieve the target power. If an increased sample size is determined to be reasonable by the investigators within the study constraints including feasibility and funding, we will seek approval from the VU IRB to increase the sample size. If the sample size is increased based on the conditional power analysis, an additional interim analysis will be scheduled to occur after 200 subjects have been studied and discharged from the hospital after surgery. At this interim analysis meeting (N=200), the DSMB will evaluate safety by analyzing any study withdrawals, any adverse events, in-hospital all-cause mortality, safety outcomes (stroke, TIA, or Q-wave myocardial infarction), and the unblinded treatment effect on the primary endpoint of Aim 1 (previously only assessed in a mock-unblinded manner for the purpose of conditional power analysis). This analysis will be completed to assess safety not efficacy of the intervention. However, if the sample size is increased, then the statistical significance thresholds for the final analyses will be adjusted to preserve the overall type-I error rate at 5%. For example, if the sample size is increased to 300, then the p-value threshold at the final analysis (for the primary aim using the Wilcoxon rank sum test) will be 0.0499 to preserve the overall type-I error probability at 5%.

There will be no possibility of ending the trial early due to futility or efficacy. All investigators and research personnel (other than the study statistician at the second interim analysis) will remain blinded to treatment assignment during all interim analyses.

We have recruited an experienced and versatile DSMB to help us carefully monitor the safety and efficacy of subject treatment. At either planned interim analysis the DSMB may recommend to continue enrollment and subject study or suspend enrollment and subject study due to safety concerns secondary to study intervention including: increased in-hospital all-cause mortality in subjects randomized to physiologic oxygenation (normoxia) such that the DSMB deems the increase is excessive compared to usual care hyperoxic oxygenation (hyperoxia), increased SAEs deemed "Probably Related" or "Possibly Related" to study intervention in physiologic oxygenation (normoxia) group compared to usual care hyperoxic oxygenation (hyperoxia) group deemed excessive, or increased incidence of stroke, TIA, or Q-wave myocardial infarction in the physiologic oxygenation (normoxia) group compared to usual care hyperoxic oxygenation (hyperoxia) group deemed excessive. The DSMB will require strong statistical evidence, corresponding to a p-value threshold of 0.001, to end the trial early due to safety concerns. The DSMB will not make any recommendations to end the study early due to efficacy or futility.

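### Sections 5.0 and 6.0 give different oxygen rules for ICU arrival, and Section 6.0 read literally makes the first ICU ventilator setting depend on arm, which could mark a subset of physiologic-arm patients

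*Combined protocol and SAP*

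**What the plan says.** Section 5.0 (Enrollment/Randomization/Blinding) sets a common rule for ICU admission: "all patients will be ventilated with 40% FIO₂ or the minimum required to maintain SpO₂ 95% if greater than 40" per cent. The same paragraph says: "The intervention is restricted to intraoperative patient management".

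Section 6.0 (Study Procedures) sets the arrival rule separately by arm:
- Hyper-oxygenation control group: "Upon arrival in the ICU, subjects will be placed on the ICU ventilator and ventilated with 40% oxygen with a tidal volume" and other settings that follow. No exception is given at arrival.
- Physiologic oxygenation group: 40%, or the FIO2 at which "the patient was being ventilated at the completion of surgery (whichever is higher").

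In both arms, Section 6.0 then leaves later ventilation, oxygen and extubation to the intensivist.

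On blinding, Section 5.0 blinds ICU nurses and intensivists and leaves anesthesiologists, perfusionists and respiratory therapists unblinded. The stated safeguard at handover is that "anesthesiologists will withhold treatment group assignment at the time of subject transfer of care at the end of surgery". Nothing is said about the end-of-surgery FIO2. Section 5.0 closes by stating that postoperative clinical care is not affected by group assignment.

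**The concern.** A site cannot follow all of these rules, because for some patients they direct different settings. Section 6.0 also ties the physiologic-arm setting to what happened in the operating room and does not do so for controls. The first number on the ICU ventilator then carries some information about the arm, and blinded staff can see it.

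Those staff decide extubation. Time to extubation and ICU length of stay are listed endpoints in Section 6.0, and both depend partly on judgement. An arm-dependent starting setting also blurs what was randomized: an operating-room strategy, or that strategy plus a different start in the ICU.

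**Working it through.** No sample size, power or alpha figure is involved, so there is no stated figure to reproduce. The check compares the texts and then illustrates how much the arrival setting could reveal.

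**Step 1: what each section directs on arrival.**

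| Patient | Section 5.0 | Section 6.0 |
|---|---|---|
| Control needing more than 40% for the SpO2 target | above 40% | 40%, then intensivist's discretion |
| Physiologic arm, above 40% at end of surgery, needing no more than 40% on arrival | 40% | the end-of-surgery value, above 40% |
| Physiologic arm, at or below 40% at end of surgery, needing more than 40% on arrival | above 40% | 40%, then intensivist's discretion |
| Control needing no more than 40%, or physiologic arm also at or below 40% at end of surgery | 40% | 40% |

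The first three rows conflict. Under Section 5.0 a setting above 40% reflects oxygen need and does not by itself mark the arm. Under Section 6.0 it can occur only in the physiologic arm.

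**Step 2: when the intervention ends.** Four descriptions are given:
- Section 5.0: confined to intraoperative management.
- Section 6.0, titration text: runs until care passes to the ICU staff.
- Section 6.0, sample time-course: ends at handover to the intensivist, after ICU admission.
- Section 12.0: ends at ICU admission.

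**Step 3: how many patients the setting could mark.** Inputs:
- N = 200 (Sections 2.0, 6.0 and 10.0).
- Equal allocation, 100 per arm. This is taken from two arms and permuted blocks of two or four.
- q = share of physiologic-arm patients above 40% at the end of surgery. The documents do not give q; it is assumed here to lie between 5% and 50%.

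Formulas under the literal Section 6.0 rules:
- Patients marked = 100 × q.
- P(physiologic | arrival at 40%) = (1 − q)/(2 − q).
- Share guessed correctly by an observer who knows the rules = 0.5 + 0.5q. All controls and all marked physiologic patients are guessed correctly; the remaining physiologic patients are not.

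| q (assumed) | Marked, of 200 | P(physiologic given 40%) | Correct guesses |
|---|---|---|---|
| 5% | 5 (2.5%) | 0.95/1.95 = 0.49 | 52.5% |
| 20% | 20 (10%) | 0.80/1.80 = 0.44 | 60% |
| 50% | 50 (25%) | 0.50/1.50 = 0.33 | 75% |

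With no information, the last two columns would be 0.50 and 50%. The setting identifies a subset, and a patient arriving on 40% tells the observer little when q is small.

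**The case against.** The strongest reply is that this is a small difference in a starting setting. Physiologic-arm FIO2 has been titrated to a saturation target during surgery, so the end-of-surgery value should often be close to the minimum needed, and later oxygen is discretionary in both arms. One sentence in Section 5.0 also exempts oxygen administration and monitoring from the promise of unaffected care. Much of this stands and limits the size of the problem. It does not remove the conflict: need may change between the end of surgery and ICU arrival, controls in Section 6.0 have no exception at all, and the closing statement of Section 5.0 on postoperative care carries no oxygen exemption.

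Four stronger readings are tempting, and the documents do not support them:
- *The arrival rule is why the intervention outlasts the operating room.* Section 6.0 already runs the intervention to transfer of care, apart from this rule.
- *The anesthesiologist must tell blinded staff the operating-room FIO2.* No text says who sets the ventilator or what is communicated. Respiratory therapists are unblinded and could set it, although no text assigns them the task. Both arms travel on the same Ambu-bag oxygen flow, so someone has to carry the value forward. That is an unaddressed gap, but it does not directly contradict withholding the assignment.
- *ICU staff can infer the arm in general.* From the arrival setting, only physiologic-arm patients above 40% are marked, and only to staff who know the Section 6.0 rules. Wider inference would need the FIO2 to be disclosed at handover, which the plan neither requires nor rules out.
- *Delirium is assessed by the ICU staff at risk of unblinding.* Section 5.0 assigns delirium to blinded physicians and research staff. Section 6.0 calls CAM-ICU standard ICU practice but does not name bedside staff as the trial's assessors.

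**Conclusion.** The point holds as an inconsistency between operative rules with a limited consequence for blinding. It is more than clerical, because the rules direct different actions and one version makes the first ICU setting depend on arm.

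The size cannot be fixed from the documents. The range of 5 to 50 marked patients rests on the assumed q, equal arms of 100, literal use of Section 6.0 and observers who know the rules. An early change by the intensivist in a control patient would weaken the signal further. The exposure is mainly to time to extubation and ICU stay. Creatinine change is a laboratory value measured by blinded technicians, so the Aim 1 primary endpoint is little affected.

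**What to change.** 1. Reconcile the ICU-arrival text in Section 5.0 with both arm descriptions in Section 6.0, so that the arrival setting does not mark the arm. The clinical content is for the sponsor to decide; this review takes no position on which rule is right.
2. State one end of intervention and use it in Section 5.0, in the titration and time-course parts of Section 6.0, and in Section 12.0.
3. State who applies the arrival setting. Either unblinded staff do so, or the setting is handed over in another way that does not disclose the intraoperative FIO2 to blinded ICU staff.

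The cost is protocol wording and a matching line in the handover instructions. Sample size, endpoints and analysis do not change.
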